Statistical Methodology	
This study has one between-subjects factor (group: MDD versus control) crossed with one within-subjects factor (time: baseline versus estradiol treatment) with the outcome (percent signal changed) assessed in response to the MID task in the structurally defined frontostriatal ROIs, including the nucleus accumbens, caudate, thalamus, frontopolar cortex, and dorsolateral prefrontal cortex. Thus, for a task/ROI combination, there is a 2-by-2 repeated measures design. We will analyze this design using an ROI analysis and mixed models with an unstructured covariance structure. To test whether perimenopausal women with MDD show reduced frontostriatal activity and motivated behavior in response to reward at baseline, we will examine group differences in BOLD signal and response latency at baseline. To measure the psychological correlates of the frontostriatal response to reward, we will examine correlations between the change in frontostriatal ROI activation and change in depressive symptoms in the MDD group between baseline and post-treatment; also within the MDD group, we will examine the correlation between frontostriatal ROI activity at baseline and the change in depressive symptoms between baseline and post-treatment. Finally, to examine whether estradiol treatment has greater effects on women with MDD than those without, we will assess whether the groups differ with respect to the change from baseline to post-treatment in percent activation in frontostriatal ROIs and response latency.
															

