**Clinical Assessments**

The Structured Clinical Interview for DSM-IV-TR Axis-I Disorders (SCID) and the Schedule for The SCID1 will be administered at baseline to determine study eligibility. The following standard measures will be administered at baseline, both fMRI sessions, and weekly clinic visits:

- The Positive and Negative Affect Schedule is a 20-item questionnaire that measures both positive affect (PA) and negative affect (NA) and is sensitive to subtle changes in affect over time.
- The Hamilton Rating Scale for Depression (HRSD) is a 21-item researcher-rated standardized scale that assesses depressive symptoms and is widely used as a measure of symptom change over time.
- The Inventory of Depression and Anxiety Symptoms (IDAS) is a 64-item self-report questionnaire that comprehensively assesses anxiety and depression symptoms on 10 subscales. The IDAS has excellent psychometric properties and has been validated for assessing reproductive mood disorders.
- The Mood and Anxiety Symptom Questionnaire - Anhedonic Depression Subscale (MASQ-AD) is a 22-item scale that assesses anhedonia (i.e., loss of interest and low positive affect). MASQ-AD scores have been associated with blunted striatal response to reward in previous studies of patients with depression.
- The Greene Climacteric Scale (GCS) is a 21-item scale that is the gold-standard measure of four domains of climacteric symptoms: vasomotor, somatic, anxiety, and depression.
- The Pittsburgh Sleep Quality Index (PSQI) is a 9-item questionnaire that measures the quality and sleep patterns in older adults. \*This measure will only be administered at the two fMRI sessions.

While the SCID and HAM-D are researcher administered, the other measures will be collected through self-report questionnaires using *Qualtrics* or paper and pencil questionnaires.

Despite the use of exclusion criteria designed to reduce risk to participants, depressive symptoms are monitored closely. Any subject who develops severe depressive symptoms (e.g., suicidal ideation) will be discontinued from the study and offered treatment paid for by the study. If inpatient hospitalization becomes

necessary as a result of the study, UNC Health Care will cover the cost. The following language has been added to the study consent form to reflect this policy:

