### **4.4 Early Withdrawal of Subjects**

#### **4.4.1 When and How to Withdraw Subjects**

Participants with significant clinical or laboratory abnormalities will be discontinued from the study prior to estrogen administration.

Adverse mood symptoms will be monitored by administering the the Hamilton Rating Scale for Depression (HRSD) at each study visit. **If suicidal thoughts or severe mood symptoms are observed at any period in the medication phase, then the suicide item of the HRSD will be administered on consecutive days for three days. Anyone who expresses suicidal thoughts with plans or intent, or who expresses concern about her ability to continue in the study, will be considered to have severe mood symptoms and be discontinued from the protocol.** In the event of the occurrence of severe mood symptoms, the protocol will be terminated. Should this step prove to be unsuccessful, conventional medication will be prescribed as needed. Although we do not anticipate severe adverse reactions, we have arranged for inpatient hospital admission in the Psychiatry Department if symptoms are otherwise unmanageable.

Any patient experiencing clinically significant side effects such as nausea, hypertension, vomiting or extreme fluid retention from the medication will have the dose titrated to achieve relief of the symptoms. If adequate relief cannot be achieved in this manner, drug treatment will be discontinued.

The determination of when and how to withdrawal subjects will be overseen by the study's principal investigator, co-investigators, and research coordinators and will be reported to the UNC Biomedical IRB.

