## 7 Statistical Plan

### 7.1 Sample Size Determination

We approximated power and sample size using a model comparing the two groups on change-scores from baseline to post-treatment. With 20 subjects per group, we have 80% power to detect effect sizes of 0.9, which represents a large effect size. Given our strong preliminary evidence and the experimental nature of the proposed research, we expect to detect statistically significant results. Previous clinical research supports our hypothesized effect size. Studies comparing participants with MDD and controls have yielded effect sizes (Cohen's  $d$ ) ranging from 1.0 to 1.56 in ventral striatum responsivity to reward 51-53. We will enroll an additional 10 participants to account for attrition, increasing the total  $N$  to 50.

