### 7.2 Statistical Methods

This study has one between-subjects factor (group: MDD versus control) crossed with one within-subjects factor (time: baseline versus estradiol treatment) with the outcome (percent signal changed) assessed in response to the MID task in the structurally defined frontostriatal ROIs, including the nucleus accumbens, caudate, thalamus, frontopolar cortex, and dorsolateral prefrontal cortex. Thus, for a task/ROI combination, there is a 2-by-2 repeated measures design. We will analyze this design using an ROI analysis and mixed models with an unstructured covariance structure. To test whether perimenopausal women with MDD show reduced frontostriatal activity (H1) and motivated behavior (H2) in response to reward at baseline, we will examine group differences in BOLD signal and response latency at baseline. To measure the psychological correlates of the frontostriatal response to reward, we will examine change in depressive symptoms between baseline and post-treatment in MDD relative to controls (H3).

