### 7.3 Subject Population(s) for Analysis

Given that we are interested in understanding the effect of estradiol on brain function, only data from protocol-compliant participants will be subjected to the study analysis.

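### H3 uses only baseline and post-treatment symptom scores, and 7.3 can drop early leavers; modelling visits 3 to 6 guards against overstated improvement if women leave because mood worsens or fails to improve

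*Combined protocol and SAP*

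**What the plan says.** Section 3.2 lists depressive symptoms as the third primary endpoint. Table 1 marks the HAM-D, IDAS, PANAS, MASQ and GCS at visits 1, 3, 4, 5 and 6, and Clinical Assessments (3.1) agrees: "The following standard measures will be administered at baseline, both fMRI sessions, and weekly clinic visits".

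For H3, section 7.2 offers one sentence: "we will examine change in depressive symptoms between baseline and post-treatment in MDD relative to controls (H3"). The Study Summary adds, for the MDD group, "we will examine correlations between the change in frontostriatal ROI activation and change in depressive symptoms in the MDD group between baseline and post-treatment".

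Section 7.2 does name a model: "We will analyze this design using an ROI analysis and mixed models with an unstructured covariance structure". The design in question has "one within-subjects factor (time: baseline versus estradiol treatment) with the outcome (percent signal changed"), which is the two-scan imaging layout.

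The only stated use of the repeated HRSD is safety: "Adverse mood symptoms will be monitored by administering the the Hamilton Rating Scale for Depression (HRSD) at each study visit" (4.4.1). Section 7.3 says "only data from protocol-compliant participants will be subjected to the study analysis" and does not define compliance. Section 4.4.2 asks women who stop hormones to go on giving self-report ratings to the end of the study. On attrition, 7.1 says "We will enroll an additional 10 participants to account for attrition", for a total of 50. No missing-data method is given.

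**The concern.** Leaving this study is linked to mood. Women who develop severe depressive symptoms are discontinued (3.1, 4.4.1), and the account of earlier experience in section 1.2 allows that attrition may be higher in women with MDD. H3a predicts improvement in that same group.

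An analysis resting on two time points, among those judged compliant, ignores the information in visits 4 and 5 about how a woman was doing before she left. If those who fail to improve leave, the remaining women look better than the treated group as a whole. The scores that could correct this are already scheduled.

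**Working it through.** **1. The plan's own figures.** Inputs from 7.1: 20 per group and a standardised difference of 0.9 on change scores. Two-sided alpha of 0.05 is assumed because none is stated.
- Normal approximation: Φ(0.9 × √(20/2) − 1.96) = Φ(2.846 − 1.960) = Φ(0.886) = 81.2%. The noncentral t gives 79.2%.
- Enrolment: 40/(1 − 0.20) = 50.

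Both agree with 7.1 and are not in dispute.

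**2. Scores collected and scores used.**

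| Visit | Symptom scales (Table 1) | Scan | Used for H3 |
|---|---|---|---|
| 1 | yes | no | unclear: baseline may be visit 1 or 3 |
| 3 | yes | yes | unclear, as above |
| 4, 5 | yes | no | no |
| 6 | yes | yes | yes |

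**3. Bias in the MDD group's change.** The documents give no correlation, dropout rate by group or dropout mechanism, so these are assumptions.
- Normal scores at visits 3 to 6, SD 1 at each visit, true visit 3 to visit 6 change of −1.00 SD, 400,000 simulated women.
- Correlation either decaying with time or constant.
- Dropout after visit 4 or 5, with log-odds rising by 1 or 2 per SD of the driving score.

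Three estimators were compared: completers' mean change; a mixed model on visits 3 and 6 that keeps early leavers' baseline; and a mixed model on all four visits (maximum likelihood). Overstatement of improvement, in SD, at correlations of 0.6 and 0.8:

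| Leaving depends on | Dropout | Completers | Two-visit model | All-visit model |
|---|---|---|---|---|
| Change since visit 3 | 10% | 0.02–0.12 | 0.02–0.06 | within 0.003 |
| Change since visit 3 | 20% | 0.04–0.22 | 0.03–0.12 | within 0.003 |
| Current level (decaying correlation) | 10% | ≤0.004 | 0.04–0.06 | within 0.002 |
| Current level (decaying correlation) | 20% | ≤0.005 | 0.07–0.12 | within 0.002 |
| Current level (decaying correlation) | 30% | ≤0.012 | 0.11–0.18 | within 0.002 |
| Nothing (random) | 10–30% | ≤0.001 | ≤0.001 | within 0.001 |

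One case in full: decaying correlation 0.6, 20% dropout, the stronger dependence on change. Completers show −1.219, so the overstatement is 1.219 − 1.000 = 0.219 SD. The two-visit model gives −1.115 and the all-visit model −0.998.

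Widening the correlation to 0.5–0.8, the completers' overstatement under change-driven leaving is about 0.02–0.13 SD at 10% dropout and 0.06–0.34 SD at 30%.

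Under level-driven leaving, selection lowers the visit 3 and visit 6 means by about the same amount, so it cancels in the difference. That rests on the equal variances and symmetric correlations assumed here.

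**4. From group change to the H3 contrast.** Bias in the contrast = bias in MDD − bias in controls. The figures above apply in full to the within-MDD change (H3a). They apply to the between-group comparison only so far as selective loss is greater in the MDD group.

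**5. Precision under random dropout.** A simulation with 25 per group and 20% dropout gave the completers' contrast a variance 5–12% larger than that of the all-visit model. A large-sample check agrees. Let Σₖ be the covariance of the first k visits and Σ that of all four. With 20% loss split over visits 4 and 5, the information is I = 0.106 Σ₂⁻¹ + 0.094 Σ₃⁻¹ + 0.80 Σ⁻¹, each inverse padded with zeros. With c = (−1, 0, 0, 1), the ratio (c′Σc/0.80)/(c′I⁻¹c) is about 1.12 for decaying and 1.07–1.08 for constant correlation.

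**The case against.** **Section 7.2 names a contrast, not an estimator.** It does not say completers only for H3. This stands as a matter of wording. Yet its mixed model is tied to the imaging outcome, and extending it to symptoms at two visits would not be enough: that version was biased under both kinds of selective leaving.

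**The written discontinuation rules turn on symptom severity, not on change.** This stands and limits the claim. A reader might infer that the plan will overstate estradiol's benefit, or attach a definite false-positive rate to it. Figures such as 0.13–0.37 SD, or a false benefit in 9–15% of null trials, require leaving driven by worsening and an assumed 30% versus 10% loss in MDD and controls. The documents give neither.

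**Early leavers are not lost outright.** A reader might infer that they contribute nothing. Section 4.4.2 keeps collecting their self-report ratings, so some could have a final IDAS or MASQ score; it is 7.3 that may exclude them. The HRSD is researcher-rated and 4.4.2 does not mention it, so the choice of scale matters.

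**Attrition may be small.** The ten extra women are an allowance, not a forecast. Section 1.2 reports under 20% loss over 12 months in a related trial and expects less here. Women who leave before visit 3 cannot be recovered by any use of visits 4 and 5.

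**The link with imaging change needs two points anyway.** True, since scans occur only at visits 3 and 6. That correlation can stay as it is.

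**Conclusion.** The point holds as a choice of analysis that should be improved. The plan leaves visits 4 and 5 out of H3, and 7.2 and 7.3 together can remove early leavers from a primary endpoint.

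Whether this biases the result depends on why women leave. Overstatement by the completers' change ranges from about nil (random or level-driven leaving) to 0.34 SD (30% dropout driven by lack of improvement). The all-visit model stayed within about 0.005 SD of the truth under every mechanism tried, which makes it the safer choice when the mechanism is unknown.

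These sizes rest on the assumed correlations, dropout rates and strength of dependence, and on leaving being explained by observed scores. No approach here protects against leaving that depends on unobserved scores. With complete data there is no gain.

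**What to change.** 1. **Section 7.2 and the Summary.** Name one symptom scale for H3 and make visit 3 the baseline. Fit a mixed model with unstructured covariance to that scale at visits 3, 4, 5 and 6, with group, visit and group-by-visit. From it, take the group difference in visit 3 to visit 6 change and the within-MDD change.
2. **Section 7.3.** For the symptom endpoint, include every treated woman with a visit 3 score. Without this, the change to 7.2 does not bring early leavers back.
3. **Ratings after discontinuation.** State whether the self-report ratings kept under 4.4.2 enter the model, since that decides whether the estimate is on-treatment or regardless of stopping.
4. **Keep** the protocol-compliant completers' change as a sensitivity analysis, and the two-point change for the correlation with imaging change.

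The cost is wording and one model, with no new visits or data. The drawbacks are that the symptom and imaging analyses will have different populations, and that the model assumes leaving depends on observed scores.

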### 7.3 Subject Population(s) for Analysis

Given that we are interested in understanding the effect of estradiol on brain function, only data from protocol-compliant participants will be subjected to the study analysis.

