### 3 Study Design

#### 3.1 General Design

Overview. This is an observational, case-control, single-center study using estradiol and progesterone to examine the role of frontostriatal hypoactivity in the pathophysiology of perimenopausal MDD (by assessing baseline differences between perimenopausal MDD and controls.) It will also allow us to measure frontostriatal responses to estradiol treatment in both perimenopausal MDD and control women. This study will include 6 study visits that will take place over the course of approximately 6 weeks. Participants will receive transdermal estradiol for 3 weeks and FMRI sessions will occur at baseline and at the end of the third week of estradiol administration. The procedures that will take place are outlined in **Table 1** and detailed below.

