### Drug Administration

Participants will receive estradiol at study visits 3-5. Participants will receive Progesterone at visit 6.

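### Section 7.3 applies one undefined compliant-only set to every analysis; its estradiol rationale does not fit the pre-drug contrasts H1a/H2a, and it leaves unsettled who enters the H3 comparison

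*Combined protocol and SAP*

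**What the plan says.** Section 7.3 is a single sentence. Because the interest is in estradiol's effect on brain function, "only data from protocol-compliant participants will be subjected to the study analysis". No other set is named, and compliance is not defined. The nearest text, section 5.5, discontinues women who are significantly non-compliant with the treatment regimen but gives no threshold.

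Section 7.2 describes the tests:
- For H1 and H2, "we will examine group differences in BOLD signal and response latency at baseline".
- For H3, "change in depressive symptoms between baseline and post-treatment in MDD relative to controls (H3").
- The model is "mixed models with an unstructured covariance structure".

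The Study Summary adds, within the MDD group, a correlation of change in activation with change in symptoms, and another of baseline activation with change in symptoms.

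On timing, section 3.1 states that "FMRI sessions will occur at baseline and at the end of the third week of estradiol administration", and section 6 that "Participants will receive estradiol at study visits 3-5". Table 1 puts the first scan at visit 3.

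On withdrawal, sections 4.4.1 and 8.5 discontinue women with severe mood symptoms. Section 4.4.2 asks discontinued women to keep giving self-report ratings to the end of the study period, but no further scan is done. Section 3.1 (Hormone Administration) holds blood samples and assays estradiol only when data collection is over.

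**The concern.** A compliant-only set can be defended where the question is how the brain responds to estradiol actually taken. H1b and H2b ask that. So does the part of H3a that links symptom change to activation change, which in any case needs a second scan. The difficulty is that section 7.3 covers the whole study analysis with that one reason.

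Two other analyses are affected. First, H1a and H2a compare the groups before treatment. Removing a woman from that comparison because she later missed patches discards a valid measurement and says nothing more about estradiol. Second, the H3 symptom comparison needs no second scan, and ratings exist for women who stop early. Whether those ratings are used depends on a word the plan does not define. Because the estradiol results arrive when the outcomes are already in hand, the cut-off for compliance could be chosen after the data are seen.

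At stake are some precision in two primary contrasts, and the interpretability of a third primary endpoint if mood withdrawals are left out.

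**Working it through.** **1. The plan's own figure.** Section 7.1 gives 80% power at d = 0.9 with 20 per group, on change scores. Alpha and sidedness are not stated; two-sided 0.05 is assumed. With noncentrality d√(n/2) = 0.9 × √10 = 2.846, 38 degrees of freedom and critical t 2.024, power is 79.2%. One-sided 0.05 gives 87.5%, which does not fit. On numbers, "We will enroll an additional 10 participants to account for attrition": 40/(1 − 0.20) = 50. The stated power and sample size reproduce.

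**2. Timing.** Table 1 and section 6 place the first estradiol supply at visit 3, the visit of the scan that section 3.1 calls baseline. The three weeks of treatment run from there to the second scan at visit 6. Section 7.2 contrasts baseline with estradiol treatment. The visit 3 scan and its response latencies are therefore pre-drug.

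**3. Precision of the baseline contrast.** The formula is the same, with 2n − 2 degrees of freedom. The plan supports its effect size with MDD-versus-control studies "ranging from 1.0 to 1.56 in ventral striatum responsivity to reward"; 0.9 is its change-score effect and is shown for reference.

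| d | 20 per group | 23 per group | 25 per group |
|---|---|---|---|
| 0.9 | 79.2% | 84.7% | 87.7% |
| 1.0 | 86.9% | 91.2% | 93.4% |
| 1.56 | 99.8% | 99.9% | 99.97% |

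If section 7.3 leaves 20 of 25 per group, the loss at d = 1.0 is 93.4 − 86.9 = 6.5 points. If 23 of 25 comply, it is 93.4 − 91.2 = 2.2 points. At d = 1.56 there is no material loss.

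**4. Bias of the baseline contrast.** This needs exclusion to be related to baseline response; unequal exclusion rates alone do not produce it. Suppose the k women ranked highest on an index correlated ρ with baseline response are dropped from 25 in the MDD group. The group mean shifts by ρ × (sum of the k largest expected normal order statistics)/(25 − k). The two largest are about 1.96 and 1.52.
- k = 1: ρ × 1.96/24 = 0.082ρ, or about 0.025 to 0.041 SD for ρ from 0.3 to 0.5.
- k = 2: ρ × 3.48/23 = 0.151ρ, or about 0.045 to 0.076 SD.

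The standard error with 23 versus 25 is √(1/23 + 1/25) = 0.289 SD, so the shift is small beside it. Both k and ρ are assumptions.

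**5. H3, only if mood withdrawals are treated as non-compliant.** The documents give no rate for these withdrawals. The illustration takes 25 women per group with no true difference in change, and drops the k MDD women highest on a withdrawal index correlated ρ with symptom change. A pooled t test is applied, and significant results in the direction of improvement are counted (nominal 2.5%; 200,000 simulated trials).

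| k | ρ = 0.5 | ρ = 0.7 | ρ = 1.0 |
|---|---|---|---|
| 0 | 2.5% | 2.5% | 2.5% |
| 1 | 3.5% | 4.0% | 5.2% |
| 2 | 4.6% | 5.9% | 8.6% |

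The corresponding mean shift is 0.04 to 0.08 SD for k = 1 and 0.08 to 0.15 SD for k = 2.

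**The case against.** The study analysis might be meant to cover only the estradiol-effect analyses. The text does not say so, and section 7 names no other population. If that is the intent, saying so is most of the remedy.

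The gap between 20 and 25 per group is a ceiling. The ten extra women are there for attrition, not non-compliance. Section 4.4.1 discontinues some before estradiol, possibly unscanned. The prior-experience summary in section 1 reports attrition below 20% in a 12-month trial and expects less here, though it allows that MDD may raise it. With 20 compliant women per group the planned number is intact. All of this stands, which is why the 2-point figure is given beside the 6.5.

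Non-compliance can also occur before visit 3, for example use of an excluded psychotropic or hormone, and that could affect the baseline scan. This stands too: the baseline set needs an eligibility condition.

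A reader might infer that the plan removes mood withdrawals and so biases H3 towards improvement. The documents do not support that. Section 5.5 ties non-compliance to the treatment regimen, and a woman withdrawn for mood has followed the protocol's own rules. On that more natural reading she is not excluded for non-compliance. Current suicidal ideation is also an exclusion at entry (section 4.2), so such withdrawals may be few. What stands is that section 7.3 does not settle the question.

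A reader might also infer from the held-back assays that compliance cannot be monitored during the study. Session review (5.5) and drug reconciliation (5.9.3) remain available. What late assay does affect is when the analysis set can be defined.

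**Conclusion.** The point holds in limited form. It is certain from the text that section 7.3 gives one undefined set, and that its rationale does not apply to the baseline contrasts. The cost for H1a/H2a is at most about 6.5 points of power at d = 1.0, about 2 points if 23 per group comply, and nil at d = 1.56, assuming two-sided 0.05 and equal groups. Bias there is likely small and requires exclusion related to baseline response.

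The H3 part is conditional on mood withdrawals being read as non-compliant. The illustrative range of about 3.5% to 8.6% false improvement, against 2.5%, rests on assumed counts and correlations. It shows direction and is not an estimate for this study. Nothing here disputes the stated power or sample size. Because the effects are modest or conditional, and section 1.1 says the study will supply pilot data, this belongs at the low end of should-fix. It is worth making because the remedy is wording on data already scheduled.

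**What to change.** Rewrite section 7.3 by hypothesis, with matching words in 7.2:

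- **(a) H1a/H2a.** All women who met eligibility through visit 3 and have a usable visit 3 scan or task record, regardless of later treatment compliance.
- **(b) H3 symptom change.** All women who received estradiol, using all available ratings, including the self-report ratings requested after withdrawal in section 4.4.2, with the compliant set as a sensitivity analysis. Use the same set for the Study Summary's correlation of baseline activation with symptom change, within the MDD group; it needs no second scan.
- **(c) H1b/H2b and the change-with-change link in H3a.** Keep the compliant set. For H1b/H2b, report beside it the section 7.2 mixed model on all available data, which can include women with only a baseline scan.
- **(d) Definition.** Fix the compliance criteria before estradiol assays are merged with outcomes, and state that protocol-directed withdrawal is not by itself non-compliance.

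The cost is a few sentences; no visit, scan or rating is added. There are two downsides: the H3 estimate is slightly diluted by non-adherence, and some ratings after withdrawal may reflect other treatment. Section 4.4.2 asks only for self-report after withdrawal, so clinician-rated HRSD scores would contribute only up to that point.
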